Protocol Title: Acceptability of HPV self-sampling tools for cervical cancer prevention in Jamaican women: A theory-based approach to culturally-tailored message design.

Version: 1A

Version Date: April 27, 2018

NCT Number: NCT03613493

1) Protocol Title

Acceptability of HPV self-sampling tools for cervical cancer prevention in Jamaican women: A theory-based approach to culturally-tailored message design.

2) IRB Review History*

N/A

3) Objectives*

The purpose of the proposed study is to increase HPV screening behaviors in Jamaican women by examining the acceptability of HPV DNA self-sampling tools, and determine the most culturally appropriate and effective message design for promoting such a tool in this context.

Specific Aim: Evaluate culturally-tailored HPV DNA self-sampling toolkit.

H1: Women who receive culturally tailored messaging will exhibit improved screening, screening-relevant knowledge, attitudes, and perceived-efficacy.

4) Background*

Low screening coverage is related to health system barriers, as well as women's attitudes and knowledge about cervical cancer screening. In a study conducted by the Ministry of Health and Environment of Jamaica in 2008, lack of uptake was found to be influenced to a significant degree by fears and misconceptions on the part of Jamaican women, including ideas that the human papillomavirus (HPV) test causes damage to the cervix. In addition, other factors impeding women in Jamaica include concerns about privacy, belief that the procedure was embarrassing, ignorance about where to get a pap test, and lack of sufficient information, fear of pain, fear of cervical cancer diagnosis, and lack of sufficient time with their doctors.

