The US Food and Drug Administration has designated HPV screening as a best practice in identifying risk of cervical cancer, over and above pap test screening, because of its high efficacy, affordability, and convenience, since it can be adapted for various settings. The HPV self-sampling tool has been shown to address issues such as privacy, and studies have shown that women feel more comfortable with this option and expressed willingness to recommend the tool to others. This adaptability has become a driving force in advocates support for the tool in hard-to-reach and poor areas. HPV self-sampling has been tested in many contexts, including resource-limited countries, and has been found to be efficacious and cost-effective. With this now fairly well-established in the literature, research questions have now focused on the best strategies for diffusion of the tools. It has been suggested that Community Health Workers (CHWs), coupled with Community-based Participatory Research (CBPR) methods are the ideal vehicle to ensure optimal uptake in community-settings. On the other hand, other studies have proposed that a mailed approach is preferred.

This current proposal aims to determine how culturally appropriate messaging within one context (Jamaica), alongside an innovation (self-sampling HPV test), might increase uptake of screening behaviors.

5) Inclusion and Exclusion Criteria*

Rationale for inclusion/exclusion criteria: This study will involve the collection of data from Jamaican women. Eligible participants will be accepted to the study on a first-come- first-serve basis. A prescreening survey in person or over the phone (see Appendix A), as well as the data from the baseline survey (see Appendix B), which will include a demographic section which will include self-reporting of age etc. (listed below) which will be an additional check for confirming eligibility for the study.

Inclusion criteria: Jamaican women, aged 30 to 65.

Exclusion criteria: women who report having had a hysterectomy, have had a history of cervical cancer, Women who are currently up-to-date on cervical cancer screening (have had a Pap in the last 3 years or have had a Pap smear/HPV co-test within the past 5 years), adults unable to consent, children, pregnant women and prisoners.

6) Number of Subjects*

Total expected: approximately 360 participants, (350 for the intervention; 10 interviews)

7) Study-Wide Recruitment Methods*

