Jamaican women will be recruited for participation in two different phases of this research project. Efforts will be made to include women from rural areas, urban areas, and varying socio economic and cultural backgrounds. Recruitment will occur in three identified low-screening regions in Jamaica (using national statistical data on screening rates per parish in Jamaica), and enrolment will take place through local community organizations as well as at community events such as health fairs.

8) Study Timelines*

An individual subject in the research is expected to participate up to maximum of 4 months. Enrolling study subjects is expected to not exceed one month prior to the actual study date. The estimated date for the investigators to complete this study is September 30, 2018. The primary data analysis will be completed by October 31, 2018. Other studies that have utilized community and government partners have been successful at recruiting a similar number of participants over a short time. For example (Barrett & Huffman, 2011) collected their entire dataset in 3 weeks in October 2007 (276 Jamaican adolescents). Another example is (Lewis-Bell et al., 2013), a cross-sectional study that

took place in April–July 2010 with 852 sexually-active Jamaican women, 16–49 years of age.

9) Study Endpoints*

The primary study endpoints are:

- Development of messages and design of HPV self-sampling tool kit.

Based on formative results from interviews (see Appendix C for interview script), messages will be designed that are culturally appropriate and tailored for any audience segments which emerge from the data. Feedback will be used to design a culturally adapted HPV DNA self- sampling toolkit for this context.

- Evaluation of culturally-tailored HPV DNA self-sampling toolkit.

Enrolled participants will complete a pre-test/baseline questionnaire which will be based on the theoretical constructs identified, and which will also be assessed in the posttest. The intervention will be considered a success when: 1) the majority of women targeted opt to return their sample, as instructed on the toolkit, for testing and, 2) upon evaluation (posttest - See Appendix C), women report higher levels of, knowledge, self-efficacy and response efficacy or positive changes in attitudes toward screening than at baseline.

10) Procedures Involved*

Interviews

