Participants will receive the HPV self-sampler at the time they complete the baseline survey with the Co-I/local study coordinator. The HPV self-sampler kit will include the collection swab and the vial for collecting and storing the specimen, and an instructional sheet that visually depicts the steps for self-sampling. 115 women will receive a culturally-targeted, fear appeal message for the HPV self-sampler kit; 115 women will receive only a fear appeal message, not targeted for the Jamaican populace; and 115 women will receive only the self-sampler tool with no message appeal (plain packaging). (Appendix G & J). The Co-I/local study coordinator will offer the HPV self-sampler accompanied by an instruction sheet on how to use the self-sampler. At this point participants will receive some sensitization on the topic, which will include: 1) health education on the importance of cervical cancer screening using a short intervention/educational script (Appendix H) and 2) motivation to encourage women to have screening using the HPV self-sampler. Women will also be informed of the following: 1) HPV infection usually is not detectable or harmful; 2) nearly everyone who has had sexual intercourse has been exposed to HPV and infection is very common; 3) a positive HPV test result does not indicate the presence of cancer and that not all women who test positive for an HPV infection will not develop advanced cancer. It will also be stressed to women that if they have not seen a doctor recently they will still need to see a provider to address other health issues, which may include a gynecologic exam. They will also be advised that if HPV obtained through self-sampling is positive, they will need follow-up medical care at clinical sites (a list of possible sites will be provided). and to package and return it by mail or to the address provided. A brief survey on intentions will then be administered (Appendix K). Participants will be asked to use the tool at home by following the instructions, The local study coordinator will follow up with participants who do not return the kit within 1 week via SMS messaging. All participants will receive the following message: "Please remember to return your HPV self-sampler kit to X location during the following times: X Y, and Z. Please ignore this message if you have already returned the kit. Thank you."

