All data will be inspected for quality assurance prior to analysis. Prior to performing statistical analysis on quantitative data, the data will be checked, screened and verified. Data checking is critical to ensure the integrity of the database. Range checks will be routinely performed, and random items from the raw data will be checked against the entered data so that mistakes can be identified. the sampling strategy for our study may be described as purposive and snowball sampling. Women will not be not randomly selected as the study was intended to capture a community-based population that meets specific selection criteria. Data will be analyzed from interviews using the constant comparison method (Corbin & Strauss, 2008). For the message design experiment, a paired t-test will be conducted to determine the difference between pre and posttests in screening behavior after exposure to the self-sampling tool; mediation analyses will be conducted to determine if change in screening knowledge, attitudes and perceived-efficacy mediated changes in screening outcomes. Mediation analyses

will be performed using ordinary least squares regression, using techniques recommended for within-subject designs (Judd, Kenny, & McClelland, 2001).

To maintain participant confidentiality, study specific ID codes are used in all study tracking and analyses. Only the Co-I/local study coordinator will have access to the files linking participants with study ID numbers.

13) Provisions to Monitor the Data to Ensure the Safety of Subjects*

All study data collected will be uploaded into the REDCap system. As previously stated, the Co-I and local coordinator have access to this system to enter participant data using an iPad or paper-based methods during interviews and site visits, and in real time during the evaluation phone call.

Furthermore, quality and completeness of data entry will be systematically checked by a data manager at regular intervals for the duration of the study. Only the Co-I has access to the raw data files entered by the Co-I/local study coordinator. De-identified data files that have been cleaned and appropriately grouped and categorized will be made available to study personnel requesting such data.

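### Three message arms are set up but none are compared: screening is tested only before versus after, which cannot show that tailoring works

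*Combined protocol and SAP*

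**What the plan says.** All references are to the combined protocol and SAP.

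- **Purpose (section 3).** The study is to "determine the most culturally appropriate and effective message design for promoting such a tool in this context". H1 reads: "Women who receive culturally tailored messaging will exhibit improved screening, screening-relevant knowledge, attitudes, and perceived-efficacy". It names no comparator.
- **Arms (section 10, Collection of Self-Samples).** "115 women will receive a culturally-targeted, fear appeal message for the HPV self-sampler kit"; 115 receive an untargeted fear appeal and 115 receive plain packaging. The same section describes "health education on the importance of cervical cancer screening using a short intervention/educational script", encouragement to screen and an SMS reminder, without distinction by arm.
- **Analysis (section 12).** For screening, "a paired t-test will be conducted to determine the difference between pre and posttests in screening behavior after exposure to the self-sampling tool". The only other quantitative analysis is mediation by ordinary least squares for within-subject designs. Neither has an arm term, and the text does not say whether the t-test is pooled or run by arm.
- **Success (section 9).** Rule 1 is that "the majority of women targeted opt to return their sample, as instructed on the toolkit, for testing". Rule 2 is that "women report higher levels of, knowledge, self-efficacy and response efficacy or positive changes in attitudes toward screening than at baseline". Neither compares arms.
- **Eligibility (section 5).** The exclusions include "Women who are currently up-to-date on cervical cancer screening".

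The supplied text does not define the screening variable (the questionnaires are in appendices not supplied). It also does not say how women are allocated to arms. The remark in section 12 that women are not randomly selected concerns sampling.

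**The concern.** Which message works best is a question about differences between arms, and the planned test estimates none. A change from before to after adds together everything that happens in between: the kit, the education, the encouragement, the reminder and the message. Only the message differs between arms.

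Running the t-test separately by arm does not repair this. A significant change in the tailored arm could meet H1 as literally worded, but it is not evidence that the tailored arm changed more than the others.

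The study could therefore meet both section 9 rules and report a significant change although the tailored package added nothing, or did worse than the other two. The two comparison arms would have been recruited and then not used for comparison.

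**Working it through.** **Inputs from the documents.** Three arms of 115, so 3 × 115 = 345 (sections 6 and 24 give 350 for the intervention). No alpha, power, effect size, SD or expected return rate is stated, so there is no planned figure to reproduce.

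**Assumptions.** Two-sided alpha 0.05; independent outcomes unless stated.

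**A. Equal improvement in every arm, so no tailoring effect.** Let d be the mean change divided by the SD of change. The paired t statistic has noncentrality d√n on n − 1 degrees of freedom; at d = 0.3 this is 0.3 × √115 = 3.22 and 0.3 × √345 = 5.57. Probability of a significant result:

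| d | tailored arm only, n = 115 | pooled, n = 345 |
|---|---|---|
| 0.2 | 57% | 96% |
| 0.3 | 89% | >99.9% |
| 0.4 | 99% | >99.9% |

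This holds for any numeric score, whatever the screening variable turns out to be.

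**B. Illustration under one possible coding.** Suppose screening means up to date or kit returned, and non-returners count as 0. Because up-to-date women are excluded, baseline is then 0 for everyone and the measure can only rise. With k kits back from n women, p = k/n, SD = √[np(1 − p)/(n − 1)] and t = p√n/SD.

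- 207 of 345 returned: p = 0.60, SD = 0.491, t = 22.7. The majority rule is met. The value is the same whether the arms split 69/69/69 or 58 (tailored)/75/74.
- In the second split the tailored arm has 58/115 = 50.4%, still a majority, with t = 10.8 and p = 4 × 10⁻¹⁹. Yet it lies 14.8 points below the untargeted arm (75/115 = 65.2%; Newcombe 95% CI 2.0 to 26.9; p = 0.023) and 13.9 points below the plain arm (74/115 = 64.3%; 1.1 to 26.1; p = 0.033). The three-arm chi-square is 6.59 on 2 df, p = 0.037.
- The test is significant from 4 kits upward: 4 of 345 gives t = 2.01, p = 0.045, and 4 of 115 gives t = 2.03, p = 0.045. The majority rule would block a success claim at that level, but it compares no arms.
- In 4,000 simulated trials at each of five return rates from 5% to 70%, equal in all arms, the pooled paired test rejected every time. In the tailored arm alone it rejected in 83% at a 5% return rate, 99.8% at 10% and 100% from 30% upward. A three-arm chi-square rejected in 4.5% to 5.4%, close to its nominal level.

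**C. What a between-arm comparison could detect.** Power = Φ{[Δ − z·√(2p̄(1 − p̄)/n)] / √[(p₁(1 − p₁) + p₂(1 − p₂))/n]}, where Δ = p₂ − p₁ and p̄ is the mean of p₁ and p₂. With n = 115, p₁ = 0.50 and p₂ = 0.681: (0.181 − 1.96 × 0.0649)/0.0637 = 0.85, which is 80% power. Detectable difference in points at 80% power:

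| assumed comparator return | alpha 0.05 | alpha 0.025 |
|---|---|---|
| 40% | 18 | 20 |
| 50% | 18 | 20 |
| 60% | 17 | 19 |
| 70% | 15 | 17 |
| 80% | 13 | 14 |

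Referral may correlate outcomes, since section 21 lets each woman name up to three others. For chains of 4 wholly within one arm the design effect is 1 + 3 × ICC. For ICC 0.05, 0.10 and 0.20 it is 1.15, 1.30 and 1.60. The effective n per arm is 100, 88 and 72, and the detectable difference from 50% at alpha 0.05 is 19.3, 20.5 and 22.6 points.

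**The case against.** - **The planned tests match H1 and the success rules.** H1 names no comparator and section 9 is written as change from baseline. That is fair, and the interviews address the cultural-appropriateness part of the purpose. The effectiveness part in section 3 still needs an arm comparison.
- **The appendices were not supplied.** True, but section 12 refers to none of them for a between-arm analysis. The point is limited to the supplied text.
- **Illustration B is chosen to make the point.** It is, and it depends on a coding the plan does not state. With a design effect of 1.15 its two p-values become 0.034 (z = 2.27/√1.15 = 2.12) and 0.047 (z = 2.13/√1.15 = 1.99). The smaller exceeds 0.025, so Holm would reject neither. Calculation A carries the argument without B.
- **Comparing tailored with each other arm does not rank all three designs, and tailored versus plain mixes tailoring with the fear appeal.** Both points are right. Tailored versus untargeted is the contrast that isolates tailoring. A full ranking needs a third comparison; at a Bonferroni level of 0.05/3 = 0.0167 about 21 points from 50% would be detectable.
- **The clustering range is one scenario.** This stands. No cap on referral waves is stated: a two-wave chain of 1 + 3 + 9 = 13 at ICC 0.10 has a design effect of 1 + 12 × 0.10 = 2.2 and a detectable difference of about 26 points. If chain members are spread over arms, the penalty shrinks or disappears.

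**Conclusion.** The concern holds and must be fixed before analysis. The analysis in section 12 is wrong for the purpose in section 3: no planned test or success rule in the supplied text compares the arms, and the paired t-test is likely to be significant whether or not tailoring has any effect. The probabilities in A rest on the assumed effect sizes, alpha 0.05 and independence; B is conditional on its coding. The conclusion that a pre/post change cannot be attributed to tailoring needs none of these assumptions. A between-arm analysis can support a causal reading only if allocation to arms is random, which the supplied text does not state.

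**What to change.** 1. Define the screening outcome as kit returned, yes or no, within a stated number of days from hand-out, with all allocated women in the denominator. The window must cover the 1-week reminder. State whether the 30-day follow-up of non-returners (section 10) and the call to them (section 20) fall inside it.
2. Report the return proportion with 95% CI in each arm. Compare the tailored arm with each of the other two by a logistic or binomial model, two-sided alpha 0.05, Holm-adjusted for two comparisons. Say that tailored versus untargeted isolates tailoring. Record who referred whom and use standard errors clustered on referral chain.
3. For knowledge, attitudes and efficacy, compare arms on posttest adjusted for baseline. Section 10 asks all women for a posttest but times it at kit return; state when non-returners are surveyed and report completion by arm.
4. State how women are allocated. If not at random, describe the comparison as non-causal and adjust for region and baseline variables.
5. Label mediation exploratory, with arm as the exposure.
6. Keep a count of withdrawals by arm, and reconcile this with the destruction of withdrawn women's data in section 14.
7. Keep the majority criterion, reported with its CI. The paired test may stay as a descriptive within-arm summary.

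**Cost.** Mostly analysis text, with no added women or survey items; kit return must already be tracked to send the reminder. The added work is a referrer ID field, an allocation statement, a posttest time for non-returners and a wording change in section 14. The drawback is limited power: differences smaller than those in the working, part C, may well be missed, and the report should say so.

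### If screening is scored yes/no, the paired pre/post t-test on screening behaviour tests only whether anyone returns a kit: 4 returns among 350 women reach p < 0.05

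*Combined protocol and SAP*

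**What the plan says.** - **Section 12 (Data Management)**, on the message experiment: "a paired t-test will be conducted to determine the difference between pre and posttests in screening behavior after exposure to the self-sampling tool". It adds a mediation analysis of changes in screening outcomes, using least squares methods for within-subject designs. It gives no definition of screening behaviour, no alpha, no sidedness and no comparison between arms.
- **Section 5** excludes "Women who are currently up-to-date on cervical cancer screening (have had a Pap in the last 3 years" or who "have had a Pap smear/HPV co-test within the past 5 years").
- **Section 10** sets up three message conditions of 115 women each; in the third, "115 women will receive only the self-sampler tool with no message appeal (plain packaging"). The kit, the education script and "motivation to encourage women to have screening using the HPV self-sampler" are described for participants generally, not for one arm. All participants are asked for a posttest, timed at return of the kit.
- **Section 9** makes success depend on two conditions: that "the majority of women targeted opt to return their sample, as instructed on the toolkit, for testing", and that posttest scores or attitudes improve on baseline.
- **Section 3, H1**: "Women who receive culturally tailored messaging will exhibit improved screening, screening-relevant knowledge, attitudes, and perceived-efficacy".
- **Section 6** gives the total as "approximately 360 participants, (350 for the intervention; 10 interviews").

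**The concern.** A paired test is informative when the measure can move in both directions and the baseline says something about where each woman started. A yes/no screening measure has neither property here. If it means up to date on screening, the entry rule sets it to no for every eligible woman. If it means having returned a kit, it is no for everyone who has not yet received one. In both cases all the variation comes from the post value, and the test asks only whether the return rate differs from zero.

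This is the only test the plan names for a screening effect. A small p-value could be reported as support for the improved-screening part of H1 even if nearly all women declined the kit. The test also has no arm term, and all three arms receive the kit and the encouragement, so a rise from zero cannot be credited to the tailored message.

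**Working it through.** The plan states no power, alpha, effect size or sample-size derivation, so it has no figure of its own to reproduce.

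**Inputs from the documents.** n = 350 (Section 6) or 3 × 115 = 345 (Section 10); one arm = 115.

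**Assumptions.** Yes/no scoring with baseline 0 for all; all women analysed and non-returners scored 0; arms pooled unless stated; two-sided alpha 0.05, with one-sided 0.05 and two-sided 0.01 as a range.

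**Formula.** With k returns among n women, the differences are k ones and n − k zeros.
- Mean difference = k/n.
- Sample variance = k(n − k)/[n(n − 1)].
- So t = (k/n) ÷ √{k(n − k)/[n²(n − 1)]} = √[(n − 1)k/(n − k)], on n − 1 degrees of freedom.

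**Smallest number of returns that reaches significance.**

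| n | alpha | k | rate | t | p |
|---|---|---|---|---|---|
| 350 | two-sided 0.05 | 4 | 1.14% | √(349×4/346) = 2.009 | 0.045 |
| 345 | two-sided 0.05 | 4 | 1.16% | √(344×4/341) = 2.009 | 0.045 |
| 115 (one arm) | two-sided 0.05 | 4 | 3.48% | √(114×4/111) = 2.027 | 0.045 |
| 350 | one-sided 0.05 | 3 | 0.86% | √(349×3/347) = 1.737 | 0.042 |
| 350 | two-sided 0.01 | 7 | 2.0% | √(349×7/343) = 2.669 | 0.008 |

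Three returns among 350 give two-sided p = 0.083, so 4 is the threshold at two-sided 0.05.

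**Check with an exact test.** Exact McNemar gives p = 2 × 0.5^k: 0.0625 for k = 5 and 0.031 for k = 6. It therefore needs 6 of 350 (1.7%).

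**Against the plan's own mark.** A majority is 176 of 350, where t = √(349×176/174) = 18.8. The pooled test turns significant at 176/4 = 44 times fewer returns; within one arm, at 58/4 = 14.5 times fewer.

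**Loss to follow-up.** With 175 women analysed, 4 returns still suffice (2.29%). If only returners complete the posttest, every difference is 1, the standard deviation is 0 and t cannot be computed.

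**True rather than observed rate.** The probability of at least 4 returns among 350 is 46% at a true return rate of 1%, 92% at 2% and 99% at 3%.

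**Other codings.**
- *Ever screened.* Some women start at 1, because Section 5 excludes only recent screening. Nobody can move from 1 to 0, so differences are still 0 or +1. The formula holds with k counted among never-screened women; the overall return rate at the threshold could then exceed 1.1%.
- *A scale score.* It can move both ways, and the argument does not apply.

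**The case against.** The strongest reply is that the outcome is undefined. Section 9 says the baseline questionnaire rests on theoretical constructs and is repeated at posttest. The questionnaires are in appendices that are not in the text available, so screening behaviour may be a scale. That stands as a condition on the whole point. Against it, kit return is the only behavioural success criterion the plan gives.

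The 1.1% figure also needs a stated alpha, pooled arms and non-returners scored 0, and the plan settles none of these. Section 20 says non-returners will be called, but not that they complete the posttest. This changes the threshold, or makes the test incomputable; neither outcome rescues it.

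Three stronger readings are tempting, and the documents do not support them:
- *The entry rule alone creates the floor.* That is so for current screening status. For kit return the baseline is zero whoever is enrolled, so the cause there is the measure.
- *The test is certain to be positive.* At a true return rate of 1% it is significant less than half the time. It is nearly automatic only from about 2% to 3% upward, with arms pooled.
- *The trial would be declared a success at 1% return.* Section 9 requires majority return as well as better posttest results, and nothing in the plan makes the t-test the success rule.

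**Conclusion.** The point holds conditionally. Under yes/no scoring, by current status or kit return, the planned test has a null that almost any use of the kit refutes. The threshold is 4 observed returns at two-sided 0.05, and 0.86% to 2.0% of 350 across the alpha choices shown. Under ever-screened scoring the baseline does carry some information, but the change remains one-directional. Only a measure free to fall as well as rise would make the paired test meaningful. The majority criterion protects the overall declaration of success; it does not protect the reading of a significant paired test as evidence for H1. That reading would be wrong whatever the return rate, because the test does not compare messages.

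**What to change.** Rewrite the analysis paragraph in Section 12:

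1. Drop the paired t-test for screening behaviour.
2. Define screening as kit return, yes/no, among all enrolled women, with non-returners counted as not screened.
3. Report the proportion with a confidence interval against the majority criterion in Section 9.
4. Compare kit return across the three message arms, to address H1. State alpha and sidedness.
5. Keep paired comparisons for knowledge, attitudes and efficacy only.
6. Re-specify the mediation with message arm as predictor and kit return as a binary outcome, in place of the within-subject change in screening. This needs posttest scores from non-returners, so say that the call to them (Section 20) includes the posttest that Section 10 already asks of all participants. The posttest follows the behaviour, so read the mediation as descriptive.

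The cost is a short rewrite and the loss of a nearly automatic positive test. No data are needed beyond those the plan already intends to collect. The replacement is more demanding: with 115 per arm, 80% power at two-sided 0.05 for one pair of arms, before any multiplicity adjustment, needs about 30% against 48%, 40% against 58.5%, or 50% against 68.5%. The lower rate in each pair is an assumption, since the documents give no expected return rate.

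### The planned mediation analysis has no message arm, so it can describe the whole programme but cannot show that the tailored message worked through knowledge, attitudes or efficacy

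*Combined protocol and SAP*

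**What the plan says.** The hypothesis in section 3 (Objectives) is about the message: "Women who receive culturally tailored messaging will exhibit improved screening, screening-relevant knowledge, attitudes, and perceived-efficacy". Section 10 (Procedures Involved, Collection of Self-Samples) sets up three groups. In the first, "115 women will receive a culturally-targeted, fear appeal message for the HPV self-sampler kit"; a second group of 115 gets an untargeted fear appeal and a third group of 115 gets plain packaging. The same section describes health education, encouragement to screen and a reminder text for late returners, without limiting any of them to one group.

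The analysis is in section 12 (Data Management). For the message design experiment it plans a paired t-test of the "difference between pre and posttests in screening behavior after exposure to the self-sampling tool", and then "mediation analyses will be conducted to determine if change in screening knowledge, attitudes and perceived-efficacy mediated changes in screening outcomes". The mediation analyses "will be performed using ordinary least squares regression, using techniques recommended for within-subject designs". Neither analysis mentions message arm, and no between-arm comparison appears elsewhere in the supplied text.

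Section 9 (Study Endpoints) says the baseline questionnaire is "based on the theoretical constructs identified, and which will also be assessed in the posttest". Its behavioural success criterion is that "the majority of women targeted opt to return their sample, as instructed on the toolkit, for testing". The Posttest Interview paragraph in section 10 places the posttest at the return of the kit. The only measure stated between handover and home use is a short survey on intentions (Appendix K, not in the supplied text).

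**The concern.** A mediation result in a message experiment will normally be read as the way the message works. Here the model contains nothing that differs between a woman who saw the tailored message and one who saw a plain package. If mediator scores rise because of the education script or the kit, and women with larger rises screen more, the analysis reports mediation whatever the package said.

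The order of measurement is a second matter, and it depends on what the outcome is. If screening outcomes means kit return, the posttest mediator in a returner is recorded after she has used and returned the kit. Using it may itself have raised her self-efficacy or changed her attitudes, so the arrow could run from outcome to mediator.

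**Working it through.** **Where the exposure lies.** There is no power or effect figure for mediation in the documents to reproduce, so the main check sets the sections side by side.

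- Package condition varies only between women (section 10).
- The mediation method is within-subject (section 12). With one condition per woman, the repeated factor can only be baseline versus posttest.
- Between those two points every group receives the kit, and the education and encouragement are described for participants generally (section 10).
- The exposure named in section 12 is the tool, which the plain-packaging group also receives.

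The pre/post contrast therefore estimates the sum of all these components. No term separates the message.

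**What the outcome could be.** Section 12 does not define it. Return is the only concrete screening endpoint in section 9. Eligibility excludes "Women who are currently up-to-date on cervical cancer screening (have had a Pap in the last 3 years" or a co-test within five years, so every eligible woman starts as not up to date and a change in that status equals its later value. Kit return likewise has no baseline value. If the outcome is instead a posttest item, mediator and outcome are recorded together, which is a weaker problem.

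**Illustration (all effects assumed).** 3 x 115 = 345 women; 2,000 trials per setting; return 50, 70 or 85%; baseline-handover and handover-posttest mediator correlations 0.3/0.5, 0.5/0.7 or 0.7/0.9; odds ratio for return 1.5 or 2 per SD of mediator. Planned model: return (0/1) on mediator change plus the centred mediator sum, with mediation declared if the mean gain and the slope are both positive at two-sided p<0.05. Comparison model: tailored v plain on the mediator, then mediator on return with arm, requiring both paths to be significant.

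| Source of a pooled 0.3 SD gain | Planned model | Arm as exposure |
|---|---|---|
| Education 0.3 SD in all, message 0 | 5.7-30.6% | 1.4-2.7% |
| Education 0.15 SD in all, message 0.45 SD in the tailored arm | 6.4-33.0% | 46-99% |

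The gains match because 0.15 + 0.45 x 115/345 = 0.15 + 0.15 = 0.30. The largest difference within a setting for the planned model is 3.7 points; the simulation standard error of such a difference near 20% is sqrt(2 x 0.2 x 0.8/2000) = 1.3 points. The 5.7-30.6% is mediation of the programme, not a type I error rate.

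The overlap depends on other components supplying the gain. At correlations 0.5/0.7, odds ratio 2 and 70% return, the planned model gives about 17% v 19% at the fixed 0.3 SD gain, but about 0.6% v 13% when education has no effect and the message effect is 0 or 0.45 SD.

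**Timing.** Assume that return is the outcome, non-returners also complete the posttest, the message has no effect, education gives 0.3 SD and the mediator does not affect return. Over all nine pairings of the listed correlations, the planned model declares mediation in:

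| Rise in mediator from kit use (SD) | Mediation declared |
|---|---|
| 0 | 1.7-3.4% |
| 0.1 | 6.6-18.3% |
| 0.2 | 17.6-58.2% |
| 0.3 | 32.4-89.0% |
| 0.5 | 70.4-100.0% |

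**The case against.** The strongest reply is that section 12 never promises to attribute mediation to the message. H1 does not mention mediation, and section 9 judges knowledge, efficacy and attitudes against baseline, so a within-subject model fits the stated success criterion. This stands in part: the model is a valid description of the programme. But section 12 introduces it as analysis of the message design experiment, and no other analysis brings in the arms.

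On timing, the same sentence in section 12 speaks of a pre/post difference in screening behaviour, which suggests a questionnaire item more than kit return. Appendix K may already contain the construct items. Both points stand, and they are why the timing issue is only conditional.

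A reader might infer three stronger things that the documents do not support:

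- **That the result would look the same whether or not the message contributed.** This holds only when other components supply the gain, as the 0.6% v 13% comparison shows.
- **That only returners are surveyed, so mediation of return cannot be estimated.** Section 10 says all participants will be asked to complete the posttest, and sections 10 and 20 have non-returners followed up or called. No posttest trigger is stated for them, but the text leans against this reading.
- **That the trial's headline conclusions fail.** No success criterion in section 9 uses mediation.

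**Conclusion.** The point holds on the text: as planned, the mediation analysis cannot tie any mediated effect to the tailored message. This follows from the design and the stated method and does not depend on any assumed effect size. The timing problem holds only if kit return is the outcome.

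The percentages rest on one mediator, assumed effects and an assumed model form. They show direction and say nothing about the likely level in this trial. The change should be made, because explaining how a tailored message works is central to a theory-based message study, but the success criteria stand without it.

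**What to change.** In section 12:

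1. Define the screening outcome.
2. For the message question, make arm the exposure: arm to mediator, adjusted for baseline mediator; then mediator to screening outcome, adjusted for arm and baseline mediator (logistic if the outcome is kit return); with a bootstrap interval for the indirect effect.
3. Name one primary contrast, for example tailored v plain. Four constructs (knowledge, attitudes, self-efficacy, response efficacy) and two contrasts would give 4 x 2 = 8 indirect effects, so treat the rest as exploratory.
4. Keep the within-subject model only if it is labelled as describing the whole programme.
5. If return is the outcome, take the mediator from the Appendix K survey, adding the construct items if they are absent, and report the later posttest as an outcome.
6. State how women are allocated, and that unmeasured mediator-outcome confounding remains possible.

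**Cost.** Analysis wording, a few more minutes at an existing sitting and one extra exposure to the items. The package must be read at handover, so message effects arising at home may be missed.

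Power is lower for the indirect effect than for one path. The arm-to-mediator difference detectable with 80% power is 2.802 x sqrt(2/115) x sqrt(1 - 0.5^2) = 0.32 SD at an assumed baseline correlation of 0.5. At that difference, simulated power for the full indirect effect is 50-70% at an odds ratio of 1.5 and 76-80% at 2. These figures use joint significance of the two paths, not the bootstrap.

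The arm-based result also needs comparable arms, and the documents do not state the allocation method. With no message effect, a non-message arm difference of 0.1 SD in the mediator gave 9-14% false mediation and 0.2 SD gave 25-41% (odds ratio 1.5-2).
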